6.6 Clinical Laboratory

Clinical labs are reported for hematology, chemistry, and urinalysis and they include the following parameters:

- **Chemistry:** glucose, calcium, sodium, albumin, total protein, potassium, bicarbonate, chloride, blood urea nitrogen (BUN), creatinine, lactate, lactate dehydrogenase (LDH), alanine aminotransferase (ALT), aspartate aminotransferase (AST), reflexive bilirubin (total, direct, indirect), alkaline phosphatase (ALP), cholesterol, triglycerides, creatine phosphokinase (CPK), high sensitivity C-reactive protein (hsCRP), high density lipoprotein (HDL), and low density lipoprotein (LDL).
- **Hematology:** platelets, white blood cells (WBCs) with differential if abnormal (% and absolute counts), hematocrit, red blood cells (RBCs), hemoglobin, , mean corpuscular volume (MCV), mean corpuscular hematocrit concentration (MCHC), and mean corpuscular hematocrit (MCH).

- **Urinalysis:** color, appearance, specific gravity, leukocyte esterase, pH, protein, glucose, ketones, blood, and nitrates. Microscopic urinalysis will be performed on samples with abnormal blood, leukocyte esterase, protein, and nitrate.

Hematology and chemistry are collected at Screening, Week 2, Week 4, Week 8, Week 12, and at Week 14 (follow-up). Values and change from baseline will be summarized by visit, for the end of treatment visit, and for the overall worst value post-baseline (which includes unscheduled visits), within each treatment group. Appendix 5 provides the directionality of the worst values for each laboratory parameter.

Urinalysis is collected at Screening and Week 12. Results will be listed by subject.

Out-of-range values will be assessed through shift tables. Each lab value will be assessed as low, normal or high based on the normal ranges provided by the central lab. Frequencies of each combination of shifts from baseline to post-baseline visits will be provided by treatment group for hematology and chemistry lab parameters only. Separate by subject listings will also be produced and out-of-range values will be flagged.

Over the course of the study, there may be some labs tests performed that were not mentioned in the protocol. These tests will not be summarized but will be included in the listings and flagged as non-protocol tests.

6.7 Vital Signs

Vital signs are assessed at Screening, Randomization, Week 2, Week 4, Week 8, Week 12 and at Week 14 (follow-up) and will consist of systolic and diastolic blood pressure (BP), heart rate (HR), respiratory rate (RR), and temperature. Vital sign measurements at each visit and the change from baseline to each post-baseline visit will be summarized by treatment group. Post-baseline vital signs will be defined as clinically notable if they meet the criterion value or both the criterion value and the change from baseline criterion listed in the table below.

Table 3 Vital Signs Clinically Notable Values/Changes from Baseline

Vital Sign	Criterion Value	Change Relative to Baseline
Pulse	≥ 100 bpm	Increase of ≥ 15 bpm
	≤ 50 bpm	Decrease of ≥ 5 bpm
Systolic blood pressure	≥ 140 mmHg	Increase of ≥ 20 mmHg
	≤ 90 mmHg	Decrease of ≥ 20 mmHg
Diastolic blood pressure	≥ 100 mmHg	Increase of ≥ 15 mmHg
	≤ 50 mm Hg	Decrease of ≥ 15 mmHg
Body temperature	≥ 37.5°C	Change of ≥ 1.1°C

The incidence of clinically notable vital signs will be summarized by time point and treatment group, and will be listed and flagged in by-subject listings. The overall post-baseline incidence of clinically notable values for each vital sign parameter, which includes values from unscheduled post-baseline visits, will also be summarized.

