2.0 INTRODUCTION

2.1 Disease Background

Psoriasis is an autoimmune disorder, manifesting in the skin, joints, or both.^[10] The disease is characterized by inflammation accompanied by hyperkeratosis resulting in inflamed, raised plaques, usually on the extensor surfaces of the body. Psoriasis provides many challenges including high prevalence, chronicity, disfigurement, disability, and associated comorbidities

LYC-30937

Clinical Protocol LYC-30937-2003

Issue Date: 30 August 2016

(such as arthritis, depression, inflammatory bowel disease, and cardiovascular diseases).^{[10], [11], [12]}

The prevalence of psoriasis in the US was estimated to be 7.4 million in 2013. The estimated total financial burden of psoriasis was estimated as 35.2 billion dollars.^[13]

The current treatment options for psoriasis are determined by the severity of the disease. For patients with severe disease that affects a large percentage of BSA, there has been robust efficacy demonstrated by biologics that block the effect of key cytokines that drive the inflammation like anti-tumor necrosis factor (TNF) α , anti-interleukin (IL) 12/23 and anti-IL-17.^[14] Patients with moderate plaque psoriasis are either treated with topical agents (eg, corticosteroids, retinoids, vitamin D analogs), for minimal BSA involvement, ultraviolet (UV) light (with or without psoralen), or oral drugs that aim to reduce inflammation through systemic effects on the immune system (eg, methotrexate and apremilast). These treatments are limited in demonstrating robust efficacy or have safety issues through local effects on the skin or systemic effects on the immune system. The current study with LYC-30937-enteric coated (EC) aims to assess the efficacy and safety of an agent that works locally in the gut with limited systemic exposure to address this continued unmet medical need.

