14. Clinically relevant hepatic, neurological, pulmonary, dermatological, ophthalmological, gastrointestinal, endocrine, psychiatric, or other major systemic disease making implementation of the protocol or interpretation of the study difficult or that would put the subject at risk by participating in the study.
15. Current active or history of clinically significant, recurrent bacterial, viral, fungal, mycobacterial or other infections (including but not limited to tuberculosis and atypical mycobacterial disease and herpes zoster), human immunodeficiency virus (HIV), or any major episode of infection requiring hospitalization or treatment with intravenous antibiotics within 4 weeks prior to the screening visit and at any time during the screening period, up through the first dose of study drug.

Note that recurring urinary tract infections are allowed.
16. History of cancer, including solid tumors and hematological malignancies (except basal cell and in situ squamous cell carcinomas of the skin that have been adequately treated with no re-occurrence for at least 1 year prior to screening).

LYC-30937

Clinical Protocol LYC-30937-2003

Issue Date: 30 August 2016

17. History of alcohol or drug abuse within 1 year prior to randomization.
18. History of or currently active primary or secondary immunodeficiency.
19. History of treatment with an investigational agent within 30 days prior to initiating screening procedures.
20. In the opinion of the investigator, the subject is not a suitable candidate for this study. For example, a medical condition that may put the subject at increased risk, likely not to be cooperative with study procedures or with completion of the study, or the inability to communicate reliably with the investigator.

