5.3 Baseline Definition

For efficacy analyses, baseline is the last assessment (including unscheduled visits) obtained before the randomization. All assessments obtained after randomization are considered as post-baseline unless otherwise specified.

For safety analyses, baseline is the last assessment (including unscheduled visits) obtained before the first dose of study treatment. All assessments obtained after the first dose of study treatment are considered as post-baseline unless otherwise specified.

Re-randomization will not be used for baseline definition and only one baseline value will be defined referring to the first randomization.

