5.4 Change from Baseline

Change from baseline (CFBL) will always be calculated as (post-baseline – baseline). It will be calculated for Subjects with both a baseline and post-baseline value as applicable.

If a baseline value has not been recorded for a parameter, then CFBL will not be calculated for that parameter, and the subject will be excluded from CFBL analysis.

Percent CFBL is the CFBL divided by the baseline value multiplied by 100. Subjects with a value of 0 at baseline or with no baseline value recorded cannot have percent CFBL calculated and they will be excluded from percent CFBL analysis.

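### The clinically notable rule in SAP 6.7 reduces to the criterion value alone, so none of the seven change-from-baseline thresholds in Table 3 affects the flag

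*SAP*

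**What the plan says.** SAP 6.7 classes post-baseline vital signs as "clinically notable if they meet the criterion value or both the criterion value and the change from baseline criterion listed in the table below". The table is Table 3, titled "Vital Signs Clinically Notable Values/Changes from Baseline". It pairs a criterion value with a change threshold in seven rows: two each for pulse, systolic pressure and diastolic pressure, and one for body temperature.

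The section defines one status and one set of outputs: incidence by time point and treatment group, flags in the by-subject listings, and "The overall post-baseline incidence of clinically notable values for each vital sign parameter", which also takes in unscheduled visits. Nothing in either document asks for the two conditions to be counted separately.

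The inputs for a working change column exist. SAP 5.3 states: "For safety analyses, baseline is the last assessment (including unscheduled visits) obtained before the first dose of study treatment". SAP 5.4 fixes change as post-baseline minus baseline.

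On a separate matter, SAP 6.6 uses Appendix 5 to choose each laboratory parameter's worst post-baseline value. Appendix 5 takes the highest value for HDL, as it does for LDL, cholesterol and triglycerides.

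**The concern.** A table that lists change thresholds, under a title that mentions changes from baseline, leads the reader to expect those thresholds to do something. As the sentence is worded, they do not. A programmer who follows the text produces a value-only table; one who guesses that both conditions were meant produces a different table from the same SAP.

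The value-only flag also counts readings that were already beyond a threshold before dosing. Such subjects can enter. The entry criteria in Protocol 4.4 set no blood-pressure or pulse limit. The general medical exclusion covers "Clinically relevant hepatic, neurological, pulmonary, dermatological, ophthalmological, gastrointestinal, endocrine, psychiatric, or other major systemic disease" only where it would hinder the study or put the subject at risk. Protocol 2.1 names comorbidities of psoriasis "such as arthritis, depression, inflammatory bowel disease, and cardiovascular diseases". With about 20 active and 10 placebo subjects, a few baseline-positive subjects can noticeably shift the notable-value counts in either arm.

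Temperature is one of the affected rows. Protocol 2.3.3 reports dose-related temperature rises in rats, so a display that responds to change is of some interest for this drug.

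**Working it through.** The plan gives no figure on this point to reproduce. The check is one of logic, followed by an illustration of scale.

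**1. Logic.** Let A = criterion value met and C = change criterion met. The written rule is A or (A and C).

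| A | C | A or (A and C) | A and C | A or C |
|---|---|---|---|---|
| 0 | 0 | 0 | 0 | 0 |
| 0 | 1 | 0 | 0 | 1 |
| 1 | 0 | 1 | 0 | 1 |
| 1 | 1 | 1 | 1 | 1 |

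The third column always equals A. Change thresholds made inert: 2 + 2 + 2 + 1 = 7.

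**2. Enumeration with the Table 3 thresholds.** All baseline/post-baseline pairs were listed on assumed grids: pulse 30-180, systolic 70-220 and diastolic 30-140 in steps of 1, and temperature 35.0-41.0 °C in steps of 0.1. This gives 4 × 22,801 + 2 × 12,321 + 3,721 = 119,567 pairs over the seven rows. The written rule differs from A in 0 pairs. Requiring value and change would remove the flag from 12,921 pairs. Accepting value or change would add it to 22,240. Either alternative alters all seven rows, so the choice of wording matters.

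**3. Examples, systolic high row (at least 140, rise of at least 20).**
- 145 to 141: change -4, flagged as written.
- 139 to 140: change +1, flagged as written.
- 110 to 139: change +29, not flagged as written, nor under value and change.

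**4. Illustration of scale; every input is assumed and there is no drug effect.** Systolic pressure was simulated at baseline and at the five post-baseline visits in SAP 6.7 (Weeks 2, 4, 8, 12 and 14). The 18 scenarios had means of 122, 126 or 130 mmHg, between-subject SD 8, 10 or 12, and within-subject SD 6 or 8, with 400,000 simulated subjects each. Both systolic rows were applied. Selected results, any visit:

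| Mean; SD between/within | As written | Value and change | Share of flagged already beyond a threshold at baseline |
|---|---|---|---|
| 122; 8/6 | 11.3% | 1.1% | 21.7% |
| 126; 8/6 | 21.6% | 1.6% | 28.4% |
| 126; 12/8 | 38.1% | 7.5% | 38.3% |
| 130; 8/8 | 46.9% | 9.1% | 33.0% |
| 130; 12/8 | 48.7% | 8.8% | 44.9% |

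Over all 18 scenarios, the written rule flags 11-49% of subjects (of 30: 0.113 × 30 = 3.4 to 0.487 × 30 = 14.6). Value and change flags 1-9% (0.011 × 30 = 0.3 to 0.091 × 30 = 2.7). Among subjects flagged as written, 18-51% were beyond a threshold at baseline.

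A one-visit version for the systolic high row assumed SD 15, mean 120-130 and within-subject correlation 0.5-0.7. It gave 9-25% as written, 1-6% for value and change, and 12-29% for value or change.

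**5. What the change column can and cannot do.** A move from 139 to 141 is a new excursion but fails the change criterion (+2). A move from 141 to 165 was present at baseline but meets it (+24). In the 18 scenarios, only about 10-33% of flagged subjects who were within thresholds at baseline ever met value and change. The other 67-90% would appear only in the first incidence, alongside subjects who were already beyond a threshold.

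**The case against.** The strongest reply is that the sentence is loose drafting for two display categories, value met and value plus change met, and that a sensible programmer would produce both. That may be what was meant. But the SAP defines one status and one incidence, and the documents do not settle whether two categories, both conditions or either condition was intended. The need for a restatement stands. The two-category form is a recommendation: it keeps the present flag intact as its first category.

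A reader might infer that Table 3 already holds what is needed to tell new excursions from old ones. It does not: its change thresholds measure the size of a change, not baseline status, as step 5 shows. That part of the objection is correct and limits what the fix can promise.

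It is also fair that little is lost as things stand. SAP 6.7 says: "Vital sign measurements at each visit and the change from baseline to each post-baseline visit will be summarized by treatment group". SAP 6.4 lists every safety parameter by subject and time point, and Protocol 6.4.2 has clinically significant changes recorded as adverse events. The temperature rule for managing subjects in Protocol 6.4.5 uses its own absolute reading. The placebo arm is exposed to the same over-inclusion. All of this stands and supports a low grade.

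Finally, the simulated percentages compare the written rule with one that the SAP does not state, using no input from the documents. They show scale and do not measure an error.

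**Conclusion.** The point holds. As worded, the clinically notable status in SAP 6.7 is the criterion value alone. All seven change thresholds are inert for the flag, the incidence tables and the listing flags, and a subject beyond a threshold before dosing is counted even when the reading has moved towards normal. This rests on the wording and needs no assumption.

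The grade is minor. Under SAP 5.1 safety analysis is descriptive, and no test, estimate or stopping rule uses the flag. Efficacy and power are unaffected. A reader might infer that safety findings would be missed; the documents do not support that, because the current rule over-includes and every reading that reaches a criterion value is flagged. The percentages above rest wholly on assumed systolic distributions and do not predict this trial.

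A reader might also infer that the HDL row in Appendix 5 is an error. The documents do not say which direction of HDL is adverse, so they contain no contradiction. By-visit values and changes, low/normal/high shift tables and flagged listings (SAP 6.6) would still show low HDL. This is a query only.

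**What to change.** Before unblinding, restate SAP 6.7 so that two incidences are reported for each parameter, by time point and overall: (1) criterion value met; (2) criterion value and change from baseline both met. Use the baseline in SAP 5.3 and the change in SAP 5.4, and give each its own listing flag. State that the second shows large changes that reach a threshold. If new and pre-existing excursions are to be separated, also tabulate the notable values by whether the subject was beyond the threshold at baseline.

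The cost is a wording edit, one extra column in the notable-value tables and, if chosen, one split by baseline status. The first incidence is the current flag, so no planned result is lost and no new data are needed.

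Secondary query: ask the sponsor to confirm that the highest value is the intended worst direction for HDL in Appendix 5, and amend the row only if it is not.

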6.8 Electrocardiogram

ECG will be assessed only at Screening and at Week 12 (End of Treatment). The following ECG parameters will be reported: heart rate, PR interval, QRS duration, QT interval, and QTc interval, and principal investigator's (PI) overall assessment of the ECG profile (normal, abnormal clinically significant, abnormal not clinically significant). The QTc interval will be presented by the Fridericia ($QTcF = QT/(RR)^{1/3}$) corrections. The ECG findings will be listed by subject, treatment group and by time point.

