3.2 Endpoints

- **Primary Endpoints (Efficacy)**

The primary efficacy endpoint of the study will be the mean percent change from baseline to Week 12 in PASI.

- **Secondary Endpoints (Efficacy)**

The secondary efficacy endpoints of the study will be:

- The proportion of subjects who achieve a $\geq 75\%$ reduction from baseline in PASI at Week 12.
- The mean percent change from baseline to Week 12 in BSA.

LYC-30937

Clinical Protocol LYC-30937-2003

Issue Date: 30 August 2016

- The proportion of subjects who achieve “cleared” (score = 0) or “minimal” (score = 1) on the static IGA at Week 12.
- The proportion of subjects who achieve a 2 step reduction on the static IGA at Week 12.

- **Secondary Safety Endpoint**

The secondary safety endpoint of the study will include AEs, PE, vital sign measurements, 12-lead ECG, and laboratory assessments.

- **Exploratory Endpoint**

Concentration of LYC-30937 will be measured in plasma and in skin as an exploratory endpoint.

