7.11 Study Hold or Stopping Criteria

The sponsor has the right to terminate the study prematurely for safety or administrative reasons. In all cases, necessary measures will be taken to ensure appropriate safety follow-up of all subjects in the trial.

Individual subjects may interrupt or stop study drug at the discretion of the investigator or medical monitor any time for safety reasons. Individual subjects must discontinue if they experience a study drug-related grade 3 (CTCAE) severity AE of special interest – see Section 6.4.6 for list of AEs of special interest.

ECGs are scheduled to be performed at Week 12 (end of treatment). An additional ECG should be performed if a subject reports symptoms of recurrent palpitations, recurrent, persistent lightheadedness or faintness, or any symptom that the investigator deems for cause. Subjects should report these symptoms to the investigator immediately and return to the clinic as soon as possible for evaluation including an ECG. Subjects will discontinue study drug if marked QT/QTc prolongation of > 500 ms or > 60 ms over baseline is present.

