8.4 General Statistical Considerations

For safety and efficacy endpoints, baseline will be defined as the last observation prior to dosing.

Continuous safety and efficacy endpoints will be summarized using mean, standard deviation, median, minimum, and maximum. Discrete safety and efficacy endpoints will be summarized by the number and percent of subjects in each category. Continuous efficacy endpoints will be analyzed using an analysis of covariance model with treatment as a factor and baseline value as a covariate. Discrete variables will be analyzed using a chi-square test. There will be no adjustments for multiplicity. Additional details of the statistical analyses will be described in the statistical analysis plan (SAP).

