5.6 Visit Windows

Data at scheduled visits will be assigned to analysis visits as defined in the Visit Window table below. To ensure that all visits have the possibility to be included in the summaries, the visit window will also classify all unscheduled and early termination visits. The analysis visits will be derived in terms of study days since the first dose of study

treatment for safety assessments, or since the date of randomization for efficacy assessments. These analysis visits will be utilized in the summary and analyses of efficacy and safety endpoints.

If a subject has more than 1 assessment in a visit window, only the assessment that is closest to the Scheduled Visit Day will be used for analysis. In case 2 assessments have the same distance from the Scheduled Day, the later assessment will be used for analysis. The early termination visit will be assigned to an analysis visit based on the window below.

Separate visit window tables are provided based on how frequently the assessments were done. For assessment which has only 1 scheduled post-baseline assessment, say at Week 12, Scheduled Visit Day will be similar as either of the tables below with visit window upper limit of Day 92, and all previous rules will apply.

No visit windows will be applied for summaries of the follow-up period data.

Table 1 Visit Windows for Assessments Done at Baseline and Weeks 2, 4, 8, and 12

Analysis Visit	Scheduled Visit Day	Visit Window for Summarization
Baseline	Day 1	≤ Day1
Week 2	Day 15	Day 2 – Day 22
Week 4	Day 29	Day 23 – Day 43
Week 8	Day 57	Day 44 – Day 71
Week 12	Day 85	Day 72 – Day 92

Table 2 Visit Windows for Assessments Done at Baseline and Weeks 4, 8, and 12

Analysis Visit	Scheduled Visit Day	Visit Window for Summarization
Baseline	Day 1	≤ Day1
Week 4	Day 29	Day 2 – Day 43
Week 8	Day 57	Day 44 – Day 71
Week 12	Day 85	Day 72 – Day 92

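### SAP 6.8 plans only a listing for ECG, with no QTcF change, flag, count or arm summary, in undeclared tension with the general rule that continuous safety endpoints are summarized

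*SAP*

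**What the plan says.** Protocol 3.2 makes ECG part of a stated endpoint: "The secondary safety endpoint of the study will include AEs, PE, vital sign measurements, 12-lead ECG, and laboratory assessments". SAP 3.7 repeats this.

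Protocol 8.4 gives the general reporting rule, and SAP 5.1 carries the same sentence: "Continuous safety and efficacy endpoints will be summarized using mean, standard deviation, median, minimum, and maximum". SAP 5.1 adds that safety analysis is confined to descriptive statistics and subject listings.

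Protocol 7.11 sets a drug-stopping limit for the individual subject: "Subjects will discontinue study drug if marked QT/QTc prolongation of > 500 ms or > 60 ms over baseline is present". It also provides for unscheduled tracings: "An additional ECG should be performed if a subject reports symptoms of recurrent palpitations", among other triggers.

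SAP 6.8 gives Screening and Week 12 as the only ECG times. It names the parameters (heart rate, PR, QRS, QT, QTcF and the investigator's overall assessment) and then specifies its output: "The ECG findings will be listed by subject, treatment group and by time point". SAP 7, which records departures from the protocol, mentions reduced SAE and death reporting but nothing about ECG.

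**The concern.** The ECG intervals are continuous measurements within a named endpoint, so the general rule would give them a summary by arm. The section written for them gives only a listing. A programmer working from 6.8 would produce no change from baseline, no marker for the two values the protocol itself treats as marked prolongation, and no comparison of arms.

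What is at stake is reporting. A rise of more than 60 ms at Week 12 or early termination that caused no symptoms, and that the investigator judged not clinically significant, could be found only by subtracting listed values. A value above 500 ms would be printed but neither flagged nor counted by arm. A moderate shift in mean QTcF on active treatment would not be shown at all.

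**Working it through.** The plan attaches no figure to ECG, so the check is mainly a comparison of texts.

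**1. Is listing-only the natural reading of SAP 6.8?** The neighbouring sections:

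| SAP section | Schedule | Planned output |
|---|---|---|
| 6.6 chemistry, hematology | Screening, Weeks 2, 4, 8, 12, 14 | values and change by visit, at end of treatment and at worst value (unscheduled included); shift tables; flags |
| 6.6 urinalysis | Screening, Week 12 | listing |
| 6.7 vital signs | Screening, randomization, Weeks 2, 4, 8, 12, 14 | values and change by arm; notable values counted and flagged; overall post-baseline count that includes unscheduled visits |
| 6.8 ECG | Screening, Week 12 | listing |
| 6.9 physical examination | Screening, Weeks 2, 4, 8, 12 | listing |

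Where the SAP means a summary, the section says so, so listing-only is the natural reading of 6.8. Some doubt remains. SAP 6.4 lists every safety parameter, including those that are also summarized, so the listing sentence in 6.8 could be read as adding to SAP 5.1 rather than replacing it.

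**2. Would applying SAP 5.1 close the gap?** In part. It would give means, SDs, medians and ranges by arm. It would not give a flag or a count against 500 ms or 60 ms.

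**3. Are the ingredients already there?** Yes. SAP 5.3 fixes the reference: "For safety analyses, baseline is the last assessment (including unscheduled visits) obtained before the first dose of study treatment". Table 1 schedules no ECG on Day 1, so in practice the baseline is normally the Screening tracing. SAP 5.4 defines change from baseline generically. Section 6.8 simply does not call on either.

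**4. Does the protocol 7.11 limit do this work during the trial?** Hardly, for completers. The one scheduled on-treatment ECG is at Day 85 (± 3 days), and planned dosing is 84 days. A stopping limit has little left to stop at that point, so comparing this tracing with the limit falls to the analysis.

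**5. Size.** Planned arms are 20 active and 10 placebo (SAP 5.2). Two scheduled ECGs each gives 2 × 30 = 60 tracings, and finding every rise above 60 ms by hand takes one subtraction per subject.

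**6. What a count could show.** With zero events in n subjects, the exact two-sided 95% upper limit is 1 − 0.025^(1/n).
- n = 20: 1 − 0.025^(1/20) = 16.8%
- n = 10: 1 − 0.025^(1/10) = 30.8%

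An empty table would therefore not exclude an effect.

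**The case against.** The strongest reply is that the protocol never promised an ECG table. Protocol 8.6, the specific safety section, names vital signs and clinical laboratory data as its examples and asks for change from baseline only where appropriate. SAP 5.1 announces listings as one form of safety output, and urinalysis and physical examination are also listed only. This stands. A reader might infer that 6.8 breaks an explicit commitment, but the documents show only tension with the general sentence in Protocol 8.4 and SAP 5.1.

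A reader might also infer that for-cause ECGs would be lost, either because 6.8 gives only two time points or because SAP 5.6 keeps one assessment per visit window, the one nearest the scheduled day. The documents do not support that for the plan as written. The time points in 6.8 can be read as restating the visit schedule. SAP 5.6 classifies unscheduled visits, and SAP 6.4 lists all safety parameters. A listing drops nothing. The window rule would matter only once a by-visit summary is added, which is a reason to word the fix with care and not a measure of the present gap.

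Many cases would surface elsewhere. Protocol 6.4.3 has clinically significant ECG changes recorded as AEs. The symptoms that prompt a for-cause ECG would normally be AEs themselves. A 7.11 stop would appear among the discontinuation reasons (SAP 6.10.1) or interruption reasons (SAP 6.10.4). This stands and narrows the gap to values not judged significant and to shifts in arm means.

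Finally, the 7.11 limits are rules for individual subjects, and no document promises a count by arm. That is fair. They are still the plan's own definition of marked prolongation, and so the natural thresholds for a flag.

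**Conclusion.** The point holds as an undeclared inconsistency between SAP 6.8 and the general rule in Protocol 8.4 and SAP 5.1, and as a cheap improvement worth making. As 6.8 stands, QTcF change is not derived, the 7.11 limits are not applied in any output, and arm-level shifts are not shown.

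The effect is modest: about 30 subjects, a listing short enough to check by hand, and other routes to the AE, disposition and interruption tables. It should not be read as a safety failing. The stopping rule and for-cause ECGs work at the site whatever 6.8 says, and Protocol 2.3.3 and 2.4 report no cardiac signal in earlier work.

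The conclusion rests on reading 6.8 as listing-only. If SAP 5.1 was meant to apply as well, the arm means are covered, and the missing flag and count remain. It also takes the 7.11 limit as applying to QTcF, the correction that Protocol 6.4.3 and SAP 6.8 both report.

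**What to change.** In SAP 6.8:

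1. Derive QTcF change from the SAP 5.3 safety baseline for every post-baseline ECG: scheduled, early termination and unscheduled for-cause.
2. Flag QTcF above 500 ms and an increase of more than 60 ms in the listing. Give n/N by arm for any post-baseline ECG, counting unscheduled ones as SAP 6.7 does for vital signs, so that the window rule in SAP 5.6 does not remove them.
3. Summarize the ECG intervals and their change at Week 12 by arm, as SAP 5.1 already states for continuous safety endpoints.

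If a listing alone is intended, say so in 6.8 and declare it in SAP 7.

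The cost is a few lines of SAP text and one small descriptive table from data already collected. No protocol change, extra ECG, visit or subject is needed, and the ECG schedule and stopping limits stay as they are. The drawback is a table likely to hold few or no events, which should be labelled descriptive so that zeros are not taken as evidence of no effect.
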